#### *Subject Evaluation of ACT*

Following each treatment session, subjects will be asked to subjectively evaluate the efficacy of the device. Subjects will be to agree or disagree with the following statement using a standard Likert scale: "This ACT technique was effective for lung clearance." At the conclusion of the study, each study subject will be asked: "Which of the studied airway clearance methods would you choose to perform on a daily basis?" Responses will be limited to each of the four studied modalities.

#### *Breath Sounds Audio Collection*

Audio recordings of non-phonated breath sounds will be collected from the subjects using a stethoscope equipped with recording capability before and after airway clearance. 25 second recordings of sounds will be recorded from up to seven locations (trachea and right and left: posterior, lateral, and anterior chest) using a flow meter to ensure standard breathing pattern. Audio files will be analyzed using a computer program designed to analyze recordings, and quantify characteristics of breath sounds (frequency, duration, and number of adventitious sounds).

#### **Data management:**

The data will be entered in REDCap, an electronic data capture program. The data entry forms will include edit checks to insure data quality. The discrepancies will be managed by the study coordinator. After reviewing the database for quality checks, the database will be frozen and exported at the end of the study for analysis.

## Data analysis:

[name], biostatistician for the UNC CF Center, has been closely involved in the study design and will be responsible for overseeing the database creation and management, as well as performing final statistical computations during data analysis.

**Primary comparison:** MCC will be visualized using a whole right lung clearance vs. time plot from immediately after isotope inhalation through 274 minutes post-inhalation. The area under this curve (AUC-Clr274), will be used to reflect “total clearance”, and will serve as the primary outcome of this study. We will compare AUC-Clr274 in huff-cough alone to AUC-Clr274 measured with each of the ACT modalities (HFCWO-vest, OPEP device, and WBV device).

**Secondary comparisons:** AUC-Clr over other intervals (i.e. 94 min and 180 min), and from other lung regions of interest (i.e. peripheral and central lung zones) will be calculated and compared in similar fashion as above. Furthermore, the change in the rate of clearance (represented by the slope of the MCC curve,  $d\text{Clr}/dt$ ) before (0-16 minutes of MCC curve;  $d\text{Clr}/dt_{0-16}$ ) versus during/after the initial ACT intervention (16 – 56 minutes;  $d\text{Clr}/dt_{16-56}$ ) will be used to compare the immediate effects of each ACT versus. huff coughs alone. The mean changes in EBC purines concentrations and FeNO, (before vs. after ACT) will be calculated. If these are found to be different from zero, a comparison between huff-cough alone and each of the ACT modalities will be made. Total sputum weights and % solids at baseline and after each ACT 40 minute period will be compared across each of the ACT modalities. We will also assess for a relationship between changes in EBC measurements, FeNO, and changes in MCC.

Means, standard deviations and 95% confidence intervals will be calculated for MCC parameters and all secondary outcome measures. A repeated measures model will be used to compare the primary and secondary outcome measures, with the subjects considered as random factors. For hypothesis one and three, MCC values from huff-cough alone will be compared to traditional ACT methods (HFCWO-vest and OPEP) and Whole Body Vibration to test the null hypothesis that there is no difference in MCC between huff-cough and a) HFCWO-vest; b) OPEP; and c) WBV. For hypothesis two, biomarker values pre and post each ACT intervention will be compared using paired t-tests to test the null hypothesis [i.e. there is no difference between candidate biomarker concentration before and after use of a) HFCWO-vest, b) OPEP, and c) WBV]. We will also compare the change in biomarker values across different methods using a repeated measure model. Finally, we will explore the strength of the relationship between MCC responses and the corresponding change in candidate biomarker values by calculating the Spearman’s Correlation Coefficient.

Breath sounds data will be collected as a pilot project, and will not be subject to statistical measures.

## Missing Data/Subject Drop Out:

Subjects that drop out before the end of visit 3 (i.e. provide only baseline data) will not be included for analysis, and will be replaced. Data from all subjects who complete at least visit 3 will be included in the analysis. Thus, partial datasets that include one of the ACT interventions will include data available allowing for the comparison of one or more ACT method to baseline. We anticipate no more than 10% drop out beyond visit 3. Per sample

[figure not shown]
size estimates below, 7 subjects are estimated to provide 80% power to detect a change from baseline, so enrolling 10 subjects should provide adequate sample size for the analyses.

**Sample size estimate:** No comparable preliminary data exists on MCC in response to ACTs. However, our lab has collected pertinent data, i.e. the effect of 2 HS doses (given 100 minutes and 4.5 hours min after isotope was inhaled) on MCC in CF patients (N=11) using the same SILP method we propose here. The mean (SD) values at baseline and after HS are shown in Table 1. We used linear interpolation to estimate the AUC-Clr270 value for these data, as this is close to the selected final imaging time point in the proposed study.

**Table 1**

	Baseline, mean (SD)	Post-HS, mean (SD)	Mean Change (SD)
AUC-Clr 180	17.4 (11.5)	30.5 (11.6)	13.1 (9.4)
AUC-Clr 360	47.4 (26.6)	89.9 (27.2)	42.4 (21.2)
Interpolated AUC-Clr 270	32.4 (19.0)	60.2 (19.1)	27.7 (15.1)

We predict that the observed mean change in AUC-Clr240 after an ACT will be somewhat smaller because this study uses a baseline that likely will be accelerated by a partially active intervention (huff cough). Therefore, we estimate a more conservative predicted effect size of 20.0 (72% of that observed after HS) with the same estimate of variability (SD 15.1) in our sample size calculations. Using these data, a dependent effect size index,  $d_z$  of 1.33 was calculated for the AUC-Clr240 variable. Using G\*Power (v3.1) and a paired, 2-tailed t-test to compare two means, we estimate that 7 subjects will be needed to detect a statistically significant difference ( $\alpha = 0.05$ ) (Figure 5). Given that we will be making multiple comparisons, wish to explore correlations between MCC and secondary outcomes, and to buffer against potential subject drop-out, we plan to enroll 10 subjects into this study.

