#### **4. Rationale for proposed study**

We intend to carry out this pilot study to determine the effect size (and variability) of cough alone and various ACT devices on MCC, signaling molecules, and sputum volume. We will also explore the correlation between MCC and signaling molecules, and compare a novel exercise device using whole body vibration to traditional ACT methods.

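### Must the plan say whether its two-sided 0.05 applies to each device contrast or to all three together?

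*Combined protocol and SAP*

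**What the plan says.** Under Data analysis, the primary comparison sets huff-cough alone against each of the vest, OPEP and WBV on AUC-Clr274, which is named "and will serve as the primary outcome of this study". The same section lists three separate nulls, "no difference in MCC between huff-cough and a) HFCWO-vest; b) OPEP; and c) WBV", to be examined in a repeated measures model with subjects as random factors. It also promises that "Means, standard deviations and 95% confidence intervals will be calculated for MCC parameters and all secondary outcome measures".

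The only significance level is in the Sample size estimate (text below Table 1). There 0.05 belongs to "a paired, 2-tailed t-test to compare two means, we estimate that 7 subjects will be needed to detect a statistically significant difference". The next sentence gives three joint reasons for going to 10: "Given that we will be making multiple comparisons, wish to explore correlations between MCC and secondary outcomes", and a buffer against drop-out. Missing Data/Subject Drop Out repeats the conclusion: "so enrolling 10 subjects should provide adequate sample size for the analyses".

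For the biomarkers the plan does write a testing condition: "If these are found to be different from zero, a comparison between huff-cough alone and each of the ACT modalities will be made". It writes none for the primary outcome. Section 4 states the purpose of the pilot as being to "determine the effect size (and variability) of cough alone and various ACT devices on MCC", along with signaling molecules and sputum volume.

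**The concern.** The plan raises multiplicity itself but answers it only with more subjects. Extra subjects raise power; they do not lower the chance that one of three tests is falsely positive. Without a stated level, the reference to multiple comparisons can be read two ways:

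- If 0.05 is per contrast, 7 subjects already reach the target for each device.
- If 0.05 covers all three, a stricter level applies and 7 might not be enough.

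The outcome could also depend on the choice. At 10 subjects in the planned model, a device with a nominal p between about 0.019 and 0.05 is significant per contrast and not significant under Dunnett. An unstated rule could in principle be settled after the data are seen, and Hypothesis 1 does claim that the devices increase clearance.

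**Working it through.** **Inputs.** From the Sample size estimate: mean paired difference 20.0, SD of the difference 15.1, two-sided 0.05, 7 needed, 10 planned. From Data analysis: three contrasts sharing one control, repeated measures model. From Missing Data: at most 10% drop-out after Visit 3, so 9 of 10 remain. Assumed, because the documents do not give them: equal variances, SD 15.1 for every contrast, correlation 0.5 between contrasts (it follows from a shared control with equal variances; range 0 to 0.9 shown), and no visit effect. The last matters because huff-cough is always at Visit 2.

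**1. The plan's own figure.** dz = 20.0/15.1 = 1.325 (the plan prints 1.33). For a paired t-test, df = n − 1 and the noncentrality is dz × √n.
- n = 6: power 73.7%.
- n = 7: noncentrality 1.3245 × √7 = 3.504, critical t (6 df) 2.447, power 83.0%.

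So 7 is the smallest number with at least 80%. The plan's figure reproduces.

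**2. False claims of benefit, each contrast at two-sided 0.05, all nulls true.** One test has a 2.5% chance of falsely favouring the device. For at least one of three, by simulation at correlation 0.5:

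| n | Paired t | Repeated measures model |
|---|---|---|
| 7 | 6.5% | 6.0% |
| 10 | 6.5% | 6.1% |

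For paired t at n = 10 the range is 4.4% (correlation 0.9) to 7.3% (correlation 0). The simple upper bound is 3 × 2.5% = 7.5%. False significance in either direction is about 12% to 13%. The rate is essentially the same at 7 and 10.

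**3. Per-contrast power under each reading.** The model has 3(n − 1) df and the same noncentrality. Dunnett critical values are 2.561 (18 df), 2.506 (24 df) and 2.489 (27 df).

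| Method | n = 7 | n = 9 | n = 10 |
|---|---|---|---|
| Paired t, 0.05 | 83.0% | 93.4% | 96.0% |
| Paired t, 0.05/3 | 60.7% | 80.1% | 86.5% |
| Model, 0.05 | 91.2% | 96.8% | 98.1% |
| Model, Dunnett | 81.6% | 92.0% | 94.9% |

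A family-wise reading needs 9 subjects only if the analysis is paired t with a Bonferroni split. In the planned model with Dunnett, 7 already exceed 80%. Ten pass in every row, and so do 9 after the expected drop-out.

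**4. What more subjects do buy.** Power to detect all three devices at 0.05 each (paired t, correlation 0.5) is 64% at n = 7, 84% at n = 9 and 90% at n = 10. Multiple comparisons is therefore a coherent power reason for enrolling more, even with no adjustment.

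**5. How often the two readings disagree** (model, n = 10, unadjusted against Dunnett). Effects of 15 and 10 are assumed values.

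| True effect | Per device | At least one of three devices |
|---|---|---|
| 20 (planned) | 3.2% | about 8.5% |
| 15 | 11.8% | about 29% |
| 10 | 16.1% | about 40% |

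**6. Price of adjusting at n = 10.** Per-contrast power falls by 98.1 − 94.9 = 3.2 points. Interval width rises by the ratio 2.489/2.052 = 1.21, about 21%.

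**The case for a change.** The strongest case for a change is that the plan names multiplicity, formally tests three nulls, and leaves the level open when one sentence would close it. The planned effect of 20 is scaled down from hypertonic saline data because no comparable data on airway clearance devices exist, so smaller effects are realistic. At those effects the two readings would often disagree on at least one device. Being a pilot justifies leaving the tests unadjusted, but it does not replace saying so.

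Part of this stands. The rule is not written down, extra subjects do not control false positives, and a clarifying sentence would do no harm.

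The rest is weaker. The plan attaches 0.05 to a comparison of two means and lists the nulls separately, one per device, so an analyst following it would test each at 0.05. The reference to multiple comparisons is one of three joint reasons, and it need not mean only these three contrasts, since the plan also compares other time intervals, lung regions, slopes, sputum and biomarkers. Nor is there much room for selective reporting: all three contrasts are named in advance on one primary outcome, and intervals are promised for the clearance parameters. A reader who prefers a family-wise standard can apply it to the published results.

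**Conclusion.** No change is needed. This is a gap that analysts fill sensibly, with a fair trade-off behind it. Writing down the per-contrast reading would record what the plan already implies. Imposing Dunnett in a 10-subject pilot, whose purpose is to estimate effects and variability for later trials, is a matter of preference.

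The exposure under the natural reading is a chance of about 6% (4.4% to 7.3%) of at least one false claim of benefit if no device works, against 2.5% for a single test. The estimates, SDs and per-contrast 95% intervals do not depend on which reading is taken. The required number of 7 is correct for the comparison described, and 10 gives 86.5% to 98.1% power per contrast across the readings checked.

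These figures rest on the plan's effect of 20 and SD of 15.1, equal variances, the stated correlation range and no visit effect. If a visit effect exists, the actual error rates are not known.
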